9.1.2.5 Haemophilia-related comorbidity

To describe hemophilia-related comorbidity in subjects receiving rFIX (RIXUBIS) (Section [9.3.2.4.4](#)).

9.1.2.6 Healthcare resource use

To describe healthcare resource use in subjects receiving rFIX (RIXUBIS) (Section [9.3.2.4.5](#)).

9.2 Setting

9.2.1 Medicinal Product

Treatment with RIXUBIS will be performed as specified in the product label and will be guided by clinical experience.

Administration, packaging, labeling, and storage for the product are described in the product label.

The investigator will record the treatment regimen, dose and dosing frequency, in the e-CRF.

9.2.2 Duration of Study Period(s) and Subject Participation

The overall duration of the study is expected to be 7 years from study initiation (i.e. first subject enrolled) to study completion. The recruitment period is planned to be approximately 3 years. The subject participation period for each individual subject is planned to be 4 years from enrollment to study completion (i.e. last study visit) unless prematurely discontinued.

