4. ABSTRACT

Title: Post Authorization RIXubis Study (PARIXS)

Rationale and background: The results derived from the RIXUBIS clinical development program suggest that RIXUBIS is efficacious, safe, and well-tolerated in adults and pediatric subjects with severe to moderately severe hemophilia B in a variety of clinical settings ^{1,2,3}.

Research question and objectives:

This study will collect data on a new product rFIX (RIXUBIS) using any therapeutic regimens administered to patients with hemophilia B in routine clinical practice.

The purpose of this study is to measure short and long-term outcomes in terms of effectiveness, safety, joint health and quality of life in routine clinical practice.

The primary objective aims to describe hemostatic effectiveness in the prevention of bleeding events in subjects with hemophilia B receiving rFIX (RIXUBIS) using any therapeutic regimen in routine clinical practice.

The secondary objectives focus on a) the description of the hemostatic effectiveness in the on-demand treatment of bleeding events, and b) safety, immunogenicity, joint-health outcomes, quality of life outcomes including acute and chronic pain and hemophilia B-related co-morbidity, physical activity and health care resources used by subjects receiving rFIX (RIXUBIS) using any therapeutic regimen in routine practice.

Study design: This study is a post-authorization, prospective, uncontrolled, non-interventional, multicenter cohort study to describe the short and long-term effectiveness, safety, immunogenicity, joint health, QoL and pain outcomes, and healthcare resource utilization in subjects with hemophilia B receiving rFIX (RIXUBIS) using any therapeutic regimen, in routine clinical practice.

Population: All patients with congenital hemophilia B receiving RIXUBIS in routine clinical practice. The observation period for each enrolled subject will be 4 years.

Variables: Effectiveness of prophylaxis, effectiveness of on demand treatment, safety and immunogenicity, joint health outcomes, health related quality of life questionnaires, acute and chronic pain assessment, assessment of physical activity, economic variables and comorbidities will be assessed.

Data sources: Data sources are patient's original clinical records and the patient's diary.

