9. RESEARCH METHODS

9.1 Study Design

This study is a post-authorization, prospective, uncontrolled, non-interventional, multicenter cohort study. Approximately 80 subjects with congenital hemophilia B will be enrolled. Subjects must be prescribed rFIX (RIXUBIS) by the treating physician before study participation. Data will be collected over a period of 4 years from the time of study enrollment. The treating physician will determine the treatment regimen, as well as the frequency of laboratory, radiological, and clinical assessment according to her/his routine. Data will be collected on routinely scheduled and emergency visits. There is no binding visit schedule, however it is recommended that the subjects have at least annual visits. Available data from these visits shall be transcribed onto the electronic case report forms (e-CRFs).

It is considered standard practice for subjects with hemophilia to maintain a diary either on paper or in an electronic form (e.g. Smart Medication) which captures FIX treatment and disease related data. A subject diary will be provided to each subject to assist with the standardization of data collection as stated in Section 9.4.2. Nevertheless, the completion of the diary is a voluntary effort by the individual subject or subject's legally authorized representative. All bleeding events and their treatment recorded in subject diaries during study participation period will be transcribed onto e-CRFs.

QoL questionnaires will be provided at baseline and on an annual basis to subjects or their legally authorized representatives.

As no hypothesis testing or interval estimation will be applied, the sample size for the study is not based on statistical considerations.

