9.5 Study Size

As no hypothesis testing or interval estimation will be applied, the sample size for the study is not based on statistical considerations. The sample size of approximately 80 evaluable subjects was selected as a reasonable number for a non-interventional study to recruit over the enrolment period planned for the study.

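### The milestone dates allow 6.67 years of data collection where section 9.2.2 needs 7, and the study size is given as about 80 both enrolled and evaluable

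*Protocol*

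**What the plan says.** **Duration.** Protocol section 9.2.2 gives three figures that fit together. Enrolment is to take about 3 years. On follow-up it says: "The subject participation period for each individual subject is planned to be 4 years from enrollment to study completion". On the study as a whole it says: "The overall duration of the study is expected to be 7 years from study initiation (i.e. first subject enrolled) to study completion". The 4 years per subject recur in section 4 ("The observation period for each enrolled subject will be 4 years") and section 9.1 ("Data will be collected over a period of 4 years from the time of study enrollment").

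**Calendar.** The milestone table in section 6 plans the start of data collection for 30 APR 2015, its end for 31 DEC 2021, and the final report for 30 JUN 2022.

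**Size.** Section 9.1 says: "Approximately 80 subjects with congenital hemophilia B will be enrolled". Section 9.5 says: "The sample size of approximately 80 evaluable subjects was selected as a reasonable number". The abstract (section 4) also uses the evaluable figure and adds that the number could rise if other countries join. Under section 9.2.4 a subject counts as enrolled once consent is signed. Section 9.3.7 lists screen failure and dropout among the reasons for ending participation. Evaluable is not defined.

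**The concern.** The recruitment period, the follow-up per subject and the data-collection window have to fit together. Sections 9.2.2 and 6 are both current text, and they give windows that differ by four months. If the milestone date governs, the last recruits cannot be observed for the 4 years that three sections state, and the cut comes from an administrative date rather than from the subjects. The place where this shows is the month-48 joint assessment in section 9.7.3.4.3, which coincides with the termination visit.

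The size statements raise a smaller question of the same kind. If about 80 people sign consent, and some then fail eligibility or contribute no usable data, the evaluable number is below 80. A site or monitor reading the protocol cannot tell which count ends enrolment.

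**Working it through.** **1. The plan's own figure.** Recruitment + follow-up per subject = 3 + 4 = 7 years. Section 9.2.2 is correct in itself.

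**2. The milestone window.** 30 APR 2015 to 31 DEC 2021 = 2437 days; 2437 / 365.25 = 6.67 years. Seven years from 30 APR 2015 is 30 APR 2022. The gap is 120 days; 120 / 30.44 = 3.9 months.

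**3. The last recruit.** Someone enrolled on 30 APR 2018, the end of year 3, can be observed until 31 DEC 2021, which is 3.67 years or 44 months instead of 48. To have 4 full years by 31 DEC 2021, a subject must enrol by 31 DEC 2017. That leaves a recruitment window of 976 days (2.67 years, about 32 months).

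**4. How many subjects.** The protocol gives no accrual pattern, so uniform accrual over 30 APR 2015 to 30 APR 2018 (1096 days) is assumed. Share enrolled after 31 DEC 2017 = 120 / 1096 = 10.9%; 0.109 × 80 = 8.8, roughly 9 subjects. Each loses between 0 and 120 days, 60 on average: 8.76 × (120 / 365.25) / 2 = 1.4 person-years out of 80 × 4 = 320, under 0.5%.

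**5. Sensitivity to the length of recruitment** (80 months of data collection, 48 months per subject, uniform accrual):

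| Recruitment (months) | Last recruit short by (months) | Subjects cut short, of 80 |
|---|---|---|
| 32 or fewer | 0 | 0 |
| 34 | 2 | 4.7 |
| 36 | 4 | 8.9 |
| 38 | 6 | 12.6 |

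**6. Effect on month 48.** Section 9.7.3.4.3 sets month 48 for HJHS, MRI and Pettersson scores, where available, and allows extrapolation for up to 0.5 years (about 183 days). The largest cut is 120 days, so the rule can reach month 48. For the very last recruit this needs an assessment in roughly the final 183 − 120 = 63 days before data close. The value is then an extrapolation, not an observation.

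**7. Report date.** 30 JUN 2022 is 181 days after 31 DEC 2021 but only 61 days after 30 APR 2022.

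**8. Size statements side by side.** The effectiveness set in section 9.7.1 takes enrolled subjects who meet all eligibility criteria. The safety set adds at least one infusion. The quality-of-life, pharmacoeconomic and joint sets add any available assessment. About 80 enrolled and about 80 evaluable therefore coincide only if essentially no one fails eligibility after consent and no one lacks usable data. The protocol gives no rate for either, so the difference cannot be quantified from it.

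**The case against.** The durations are hedged as expected, planned and approximate, and the milestones are planned dates. If recruitment finishes within 32 months, no one is cut short. This stands: the shortfall is conditional. It does not reconcile the text, because no section says that recruitment ends at 32 months. Any slip runs the other way: the 7-year clock starts at first enrolment, which section 10.3 places after ethics approval, so a first enrolment later than 30 APR 2015 widens the gap.

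The consequences are also small, and three stronger readings that a reader might infer are not supported:

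- *That 80 evaluable requires no loss over 4 years.* The protocol never ties evaluable to completing 4 years. The effectiveness set keeps all eligible enrolled subjects. ABR is estimated for non-completers with at least 90 days on regimen, and the regimen median is substituted for those without an interval assessment. The other sets need only some assessment, and sections 9.2.7 and 9.3.7 use data up to withdrawal or discontinuation. Later dropout therefore does not remove a subject, and 4-year dropout rates say nothing about the evaluable number.
- *That month-48 quality-of-life and resource-use summaries lose the late recruits.* Sections 9.7.3.4.4 and 9.7.3.4.5 summarise change to follow-up visits and name no month-48 summary.
- *That exact 48-month data were otherwise assured.* Section 9.1 has no binding visit schedule.

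Finally, the size has no statistical basis and is given as approximate, so no power or precision target is missed.

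**Conclusion.** The calendar conflict holds. Sections 9.2.2 and 6 differ by 120 days. If recruitment takes the full 3 years from 30 APR 2015 and accrual is uniform (an assumption), about 11% of subjects, roughly 9 of 80, lose up to 4 months of the stated observation, and their month-48 joint scores are extrapolated at best. The primary endpoint is hardly touched: ABR is a rate over observed days, and even the last recruit would have about 44 months if he or she stays in the study.

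The size mismatch also holds, as a matter of definition. One figure serves for two different counts, with no allowance for screen failures after consent or for subjects with no usable data. Both points are inconsistencies worth correcting; neither undermines the primary analysis.

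**What to change.** **Calendar, one of two.**

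- Move the end of data collection in section 6 to at least 30 APR 2022, stated as 7 years from the actual first enrolment, and move the final report by the same interval. Cost: a report about 4 months later.
- Keep 31 DEC 2021 and state in section 9.2.2 that recruitment closes on 31 DEC 2017, with the recruitment and overall durations changed to match. Cost: a recruitment window about 4 months shorter. At the pace implied by 80 subjects in 1096 days, 976 days would bring in 80 × 976 / 1096 = about 71, so sites would have to recruit faster or a lower number be accepted.

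**Size.** Use a single statement, approximately 80 enrolled, in sections 4, 9.1 and 9.5. Define evaluable by reference to the analysis sets in section 9.7.1, and restate the evaluable number as somewhat lower, with the assumed share of screen failures and subjects without usable data given. Cost: wording only and a lower stated evaluable number; no additional subjects are needed.

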9.2.3 Subject Selection Criteria

9.2.3.1 Inclusion Criteria

Subjects who meet **ALL** of the following criteria are eligible for this study:

1. Subject has congenital hemophilia B (FIX level $\leq 5\%$)
2. Subject is prescribed rFIX (RIXUBIS) by the treating physician as part of routine clinical practice
3. Subject or subject's legally authorized representative provides informed consent.

9.2.3.2 Exclusion Criteria

Subjects who meet **ANY** of the following criteria are not eligible for this study:

- Known hypersensitivity or presence of any contraindication to rFIX
- Disseminated intravascular coagulation (DIC)
- Acute thrombosis or embolism (including myocardial infarction)
- Other severe concomitant clinically relevant conditions or bleeding disorders that in the investigator's opinion precludes the inclusion of the patient.

9.2.4 Informed Consent and Enrollment

Any patient who directly, or indirectly through a legally authorized representative, provides informed consent (ie, signs and dates the informed consent form (ICF) or assent form, if applicable) is considered to be enrolled in the study.

9.2.5 Subject Identification Code

The following series of numbers will comprise the subject identification code (SIC): protocol identifier (251401) to be provided by the MAH, 3-digit study site number (eg, 002) and 3-digit subject number (eg, 003) reflecting the order of enrollment (ie, signing the informed consent form). For example, the third subject who signed an informed consent form at study site 002 will be identified as Subject 251401-002-003. All study documents (eg, e-CRFs, clinical documentation, etc.) will be identified with the SIC. Alternative uniquely coded SIC(s) is permitted as long as it does not contain a combination of information that allows identification of a subject, in compliance with laws governing data privacy.

9.2.6 Screening and Follow-up

The study site is responsible for maintaining an enrollment log that includes all subjects enrolled. Data on recruited subjects are expected to be collected during the routine visits. The data will be prospectively collected at the sites and recorded onto e-CRFs from hospital medical records - the subject diaries will be completed by the subjects at home. Details on the assessments/data to be recorded for screening and follow-up, can be found in [Table 2](#).

Table 1 Schedule of Study Procedures and Assessments^a				
Procedures / Assessments	Screening Visit	Interim Visits^e	Annual Visits	Termination Visit
Informed Consent ^b	X			
Eligibility Criteria	X			
Medical History including Hemophilia treatment history	X			
Rixubis Treatment Regimen	X	X	X	X
Non-drug Therapies	X	X	X	X
Concomitant Medications	X	X	X	X
Physical Examination	X	X	X	X
Vital Signs	X	X	X	X
Joint Evaluation	X	X	X	X
Chronic Pain Assessment	X	X	X	X
Surgical Procedures		X	X	X
Subject Diary	D	R/D	R/D	R
Adverse Events ^c		X	X	X
Hemostatic Effectiveness		X	X	X
Health Resource Use	X	X	X	X
HRQoL Questionnaires	X		X	X
Acute Pain Assessment ^d		X	X	X
Daily Activity Level	X		X	X
End of Study Form				X

^a Standard procedure according to routine clinical practice

^b Occurs at enrollment

^c AEs will be collected whenever they occur. Each AE will be evaluated by the investigator for seriousness (Section 11.1.1.1), severity (Section 11.1.2.1) and causal relationship (Section 11.1.2.2)

^d As part of the diary

^e As needed

Table 2 Clinical Laboratory Assessments				
Procedures / Assessments	Screening Visit	Interim Visits^b	Annual Visits	Termination Visit
Inhibitor to FIX ^a	X	X	X	X
FIX clotting assay ^a	X	X	X	X

^a Standard procedure according to routine clinical practice

^b As needed

The following data will be collected at the screening visit according to routine clinical practice:

- Year of birth
- Gender
- Height
- Weight
- If a pediatric patient: percentile of height growth curve and weight growth curve
- Pulse rate
- Blood pressure
- Medical history
- History of hypertension
- Baseline FIX levels
- Family history of inhibitors.
- History of inhibitor development
 - Date(s) of inhibitor detection
 - Total FIX EDs at time of inhibitor detection
Where the exact numbers of ED is not available, one of the following ranges should be selected: 0, 1-4, 5-20, 21-50, 51-100, 101-150 or >150.
 - FIX product used at the time of inhibitor detection
 - FIX regimen used at the time of inhibitor detection
 - Maximum historical titer
 - Local laboratory cut off value for positive inhibitor titer
 - History of ITI therapy, if any, including FIX product and regimen used.
 - Date(s) of inhibitor disappearance
 - Most recent FIX inhibitor test results.
- Current RIXUBIS treatment
 - Dosage and dosing intervals
 - Regimen start date

- Total EDs to RIXUBIS at screening visit
Where exact numbers of EDs is not available, one of the following ranges should be selected: 0, 1-4, 5-20, 21-50, 51-100, 101-150 or >150.
- FIX product used prior to RIXUBIS treatment initiation (maximal retrospective time-period of 12 months before treatment initiation)
 - Name of product, dosage and dosing interval
 - Regimen start and end date
 - Total EDs to FIX products at screening visit
Where exact numbers of EDs is not available, one of the following ranges should be selected: 0, 1-4, 5-20, 21-50, 51-100, 101-150 or >150.
- Sporting activities (type and frequency)
- Ambulatory status, including need for ambulatory assistance devices such as leg braces, cane, crutches, or wheelchair
- Number of bleeding episodes (ABR and annualized joint bleeding rate (ABJR)) categorized by severity within the last 12 months.
- Status of joint health as assessed by physical exam at study enrollment
+ Musculoskeletal evaluation of target joints using HJHS within the last 5 years prior to study enrollment.
- Status of joint health assessed by imaging techniques (e.g. MRI or X-ray)
+radiological evaluation of any joints using the Petterson score within the last 5 years prior to study enrollment.

The following data, if available will be collected at interval and termination visits:

- Total EDs to RIXUBIS since the last visit
- Current RIXUBIS treatment regime (if changed):
 - Dosage and dosing intervals
 - Regimen change date
- Height, Body weight
- FIX inhibitor titer
- Bleed occurrence, including location, etiology, and severity

- Status of joint health as assessed by physical exam
+ Musculoskeletal evaluation of target joints using the HJHS.
- Status of joint health as assessed by imaging techniques (e.g. MRI, X-ray)
+ Radiological evaluation of any joints using the Pettersson score.
- HRQOL measures, surgical data and activity levels (including sporting activities)

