RIXUBIS was investigated for prophylactic use in pediatric PTPs aged <12 years with severe (FIX level < 1%) or moderately severe (FIX level 1-2%) hemophilia B. The purpose of this prospective clinical trial was to assess the safety, hemostatic efficacy, and PK profile of RIXUBIS which was administered as prophylaxis twice a week over 6 months, and on-demand for treatment of bleeds. Safety was assessed by the occurrence of related AEs, thrombotic events and immunologic assessments. Efficacy was evaluated by ABR, and by treatment response rating (excellent, good, fair, none). PK was assessed over 72 hours.

None of the 23 treated subjects experienced an SAE or AE related to treatment. There were no thrombotic events, and no inhibitory or specific binding antibodies against FIX, rFurin or CHO protein. Twenty-six bleeds (19 non-joint vs. 7 joint bleeds) occurred, of which 23 were injury-related (mean ABR 2.7 ± 3.14 , median 2.0). Twenty subjects (87%) did not experience any bleeds of spontaneous etiology. Hemostatic efficacy of RIXUBIS was excellent or good for >96% of bleeds (100% of minor, 88.9% of moderate, and 100% of major bleeds); the majority (88.5%) resolved after 1-2 infusions. The PK analysis revealed that the incremental recovery (IR) 30 minutes after infusion was consistent over time. IR was associated with age, increasing IR was observed with increasing age (mean IR of all subjects (n=23): 0.665 ± 0.1632 (median 0.685); subjects <6 years (n=11): mean IR 0.586 ± 0.1320 (median 0.591); and in subjects between 6 and 12 years mean IR was 0.731 ± 0.1615 (median 0.714). Longer $T_{1/2}$ and lower IR were observed in younger children (<6 years) compared to the older age group. In summary, RIXUBIS was efficacious in preventing and controlling bleeds, and was safe in pediatric patients aged <12 years with hemophilia B ^{9;10;11}.

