9.3.2.3 Joint Health/Function Outcomes

(see [APPENDIX 2](#))

The health status of the joints (e.g. knee, ankles, elbows) will be further assessed by the following endpoints, where available

- HJHS ¹⁷
- Radiographs, using the Pettersson scale ¹⁸
- Magnetic resonance imaging scoring system
- Total number of target joints ¹⁹
- Number of invasive surgical procedures, such as (not exclusively orthopedic) surgery, radiosynovectomy, and chemosynovectomy per year per patient
- Incidence of new target joints

A target joint is defined as a joint in which at least 3 or more spontaneous bleeds into a single joint within a consecutive 6 month period. Where there have been ≤ 2 bleeds into the joint within a consecutive 12 month period the joint is no longer considered a target joint ¹⁹.

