The Hemophilia Joint Health Score (HJHS)¹⁷ was developed by the International Prophylaxis Study Group (IPSG) as a new scoring system for musculoskeletal evaluation optimized for use in children with no or minimal joint disease. The HJHS is better suited for children aged 4–18 years and all patients on primary prophylaxis than the Gilbert score, which was found to be too insensitive to identify earliest signs of joint disease. The HJHS includes the following parameters: swelling, duration of swelling, muscle atrophy, joint pain, crepitus on motion, flexion loss, extension loss, strength and global gait. The HJHS measures joint health, in the domain of body structure and function (i.e. impairment), of the joints most commonly affected by bleeding in hemophilia: the knees, ankles, and elbows. It can be used when there is a need for orthopedic intervention, or as an outcome measure of physiotherapy interventions. It is appropriate for monitoring joint change over time or assessing effectiveness of treatment regimens in children receiving both prophylactic and on-demand therapy. The HJHS 2.1 provides a total score (higher score is worse; max=124), joint specific scores, and a global gait score. See [Table 5](#). The HJHS total score, calculated from the Sum of Joint Totals and Global Gait Score will be collected during screening, annual, and termination visits or whenever the treating physician deems it appropriate.

Table 5 Hemophilia Joint Health Score (HJHS) for assessing Joint Impairment	
Swelling	0 = no swelling 1 = mild 2 = moderate 3 = severe
Duration (swelling)	0 = no swelling or < 6 months 1 = ≥6 months
Muscle Atrophy	0 = none 1 = mild 2 = severe
Joint Pain	0 = no pain through active range of motion 1 = no pain through active range, only pain on gentle overpressure or palpation 2 = pain through active range
Crepitus on Motion	0 = none 1 = mild 2 = severe
Flexion Loss	0 = < 5° 1 = 5° - 10° 2 = 11° - 20° 3 = > 20°
Extension Loss (from hyperextension)	0 = < 5° 1 = 5° - 10° 2 = 11° - 20° 3 = > 20°

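### The protocol gives three incompatible scopes for the HJHS: target joints (9.2.6), the six-joint total (Appendix 2) and a parameter subset with a non-HJHS item (9.7.3.4.3)

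*Protocol*

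**What the plan says.** Section 9.2.6 lists what sites record. At screening the HJHS item is "Musculoskeletal evaluation of target joints using HJHS within the last 5 years prior to study enrollment"; at interval and termination visits it is "Musculoskeletal evaluation of target joints using the HJHS". The imaging item beside it is wider: "Radiological evaluation of any joints using the Pettersson score".

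Appendix 2 describes the HJHS as a measure "of the joints most commonly affected by bleeding in hemophilia: the knees, ankles, and elbows", gives a maximum of 124, and states: "The HJHS total score, calculated from the Sum of Joint Totals and Global Gait Score will be collected during screening, annual, and termination visits". Further assessments are left to the physician's judgment.

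Section 9.3.2.3 names the HJHS as a joint-health endpoint where available, with no limit to target joints. It also defines the target joint. A joint enters with at least 3 spontaneous bleeds in a consecutive 6 months; with 2 or fewer bleeds in a consecutive 12 months, "the joint is no longer considered a target joint".

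Section 9.7.3.4.3 summarizes the HJHS at 0, 12, 24, 36 and 48 months, with linear interpolation and limited extrapolation. It restricts the summary to pain, bleeding and physical-examination parameters and does not name the total score.

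**The concern.** Section 9.2.6 is the list a site or e-CRF designer would work from, and its HJHS item is narrower than the score that Appendix 2 says will be collected. A joint that is not examined at the visit cannot be recovered later, so no analysis rule can repair this.

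The limit also depends on an outcome. Target status is defined by bleeding, and prevention of bleeding is the primary objective. Under a literal reading of 9.2.6, bleeding decides whether a joint is scored and, across visits, which joints make up the score. The protocol expects target status to change: new target joints are an outcome in 9.3.2.3 and are summarized in 9.7.3.3. Interpolating a score between visits, as 9.7.3.4.3 plans, presumes that the same quantity was measured at each of them.

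Appendix 2 further describes the HJHS as optimized for children with little or no joint disease, a group in which few joints would be expected to meet the target-joint definition.

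**Working it through.** **Inputs.** Item maxima from Table 5 (Appendix 2): swelling 3, duration of swelling 1, muscle atrophy 2, joint pain 2, crepitus 2, flexion loss 3, extension loss 3, strength 4, and global gait 4 (scored once per subject). Joints: knees, ankles and elbows, so six. Stated maximum: 124.

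**Step 1: reproduce the protocol's figure.**

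Per joint: 3 + 1 + 2 + 2 + 2 + 3 + 3 + 4 = 20.

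Total: 6 x 20 + 4 = 124, which agrees with Appendix 2. The total score therefore needs all six joints and gait.

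**Step 2: what a literal reading of 9.2.6 can supply.** With k target joints scored, the joint points are at most 20k, or 20k + 4 if gait is also scored.

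| k | Joint points, max | With gait, max | With gait, share of 124 |
|---|---|---|---|
| 0 | none | 4 | 3% |
| 1 | 20 | 24 | 19% |
| 2 | 40 | 44 | 35% |
| 3 | 60 | 64 | 52% |
| 6 | 120 | 124 | 100% |

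Only when all six joints are target joints do the 9.2.6 data give the Appendix 2 total. Section 9.2.6 does not mention gait, so the row for k = 0 may be no HJHS value at all.

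**Step 3: effect of a change in target status.** Suppose scores are summed over the joints that are target joints at each visit. A joint with unchanged score s that loses target status changes the sum by -s, which lies between 0 and -20.

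Illustration with assumed scores, since the protocol gives none: two target joints at 8 and 6, four other joints at 2 each, gait 1, and nothing changes between visits.

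- Six-joint total: 8 + 6 + 4 x 2 + 1 = 23 at both visits.
- Sum over current target joints: 8 + 6 + 1 = 15, then 8 + 1 = 9 once the joint scoring 6 loses status, an apparent improvement of 6 points.
- Sum over the baseline target joints, kept fixed: 15 at both visits, so no artefact.

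**Step 4: the analysis section against Table 5.** The Table 5 items are the nine listed above. Bleeding is not among them, so the summary described in 9.7.3.4.3 matches neither the Appendix 2 total nor a subset of Table 5 items.

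**Not needed.** No error rate, power or effect size enters. Section 9.5 says "As no hypothesis testing or interval estimation will be applied, the sample size for the study is not based on statistical considerations", and the point does not depend on sample size.

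**The case against.** The strongest reply is that 9.2.6 is the odd one out. It does not say that the HJHS is recorded for target joints alone. Appendix 2 states outright that the total is collected, and Sections 9.1.2.3 and 9.3.2.3 describe the HJHS without a target-joint limit. A reader might infer that the HJHS is recorded solely for target joints; the documents do not establish that. They show sections in conflict, and every consequence above depends on sites following 9.2.6 over Appendix 2. This part of the reply stands.

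A reader might also infer that a spurious improvement is built into the endpoint. It is not. It arises only if scores are summed over current target joints, and the protocol states neither that rule nor a fixed baseline set. Such a rule could properly sit in the SAP, which is not at hand. The set of joints examined is a protocol matter, however, and a later document cannot restore missing examinations.

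It is tempting to size the problem from Section 7.2: "Twenty subjects (87%) did not experience any bleeds of spontaneous etiology" in the pediatric study, and 24 of 56 (43%) prophylaxis subjects without any bleed in the pivotal study. Neither figure measures the share left unscored. Both come from subjects on prophylaxis, whereas this study admits any regimen and follows subjects for 4 years. A joint that qualified before the study period may also keep its status through 6 months without a spontaneous bleed.

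Finally, the stakes are limited. This is a secondary, descriptive outcome collected where available, and 9.2.6 separately records joint status by physical examination with no target-joint limit. Subjects without a target joint are therefore not without joint data.

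**Conclusion.** The contradiction is real and should be corrected. Sections 9.2.6 and 9.7.3.4.3 and Appendix 2 specify three different things under the name HJHS and cannot all be followed. That much rests only on the text and on 6 x 20 + 4 = 124.

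The consequences are conditional. If 9.2.6 is followed literally, subjects without a target joint have no joint score, one target joint reaches at most 24 of 124 with gait, and selection of joints depends on bleeding. If, in addition, the sum runs over current target joints, a change in status alone can move it by up to 20 points per joint. How many subjects would be affected cannot be estimated from the protocol.

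**What to change.** In 9.2.6, in both the screening and the follow-up HJHS items, replace *target joints* with *both elbows, knees and ankles, plus global gait*, and keep the score as if available. In 9.7.3.4.3, name the same score as Appendix 2, built from Table 5 items, and remove bleeding from the list of HJHS parameters.

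Where a site scored only some joints, compute change only over joints scored at both visits and do not report the result as an HJHS total.

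Cost: a slightly longer examination where only target joints would have been scored, and a small change to protocol and e-CRF wording. No visit is added.
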